5.1.5 Patient Position

To decrease the risk of aspiration and nosocomial pneumonia, patients will be maintained in the semi-recumbent position (head of bed raised 30-45 degrees) at all times possible (Drakulovic, 1999; Mentec, 2001; Spain, 1999). Exceptions to the semi-recumbent position will include times when tube feeds are turned off because a patient is: having a bedside procedure performed, bathing, or hypotensive requiring flat or reverse Trendelenburg positioning.

5.1.6 Holding or Interrupting Enteral Feeds

Enteral feeds held for less than 30 consecutive minutes will not be considered interrupted, but when held for 30 minutes or more should be reported as interrupted on the case report form.

Enteral feeds should be held for no more than 4 hours prior to procedures, including surgical procedures in the operating room, and in anticipation of extubation. Alternatively, feedings can be continued up to the time of the procedure or extubation and the gastric volume, including enteral feeds, can be removed using manual suction through a 60 cc syringe. Post-procedure, or if patient deemed not ready for extubation, feedings should be restarted at the prior rate.

If enteral feeding is stopped for any reason other than gastrointestinal intolerance (see Gastrointestinal Intolerances, Section 5.1.7), then tube feeds are to be restarted at prior rate.

5.1.7 Gastrointestinal Intolerances

The action taken if a patient has one of the following gastrointestinal intolerances will be standardized. However, the patient's primary medical team will determine whether or not the patient fulfills the criteria for meeting the definition of the specific gastrointestinal intolerance.

5.1.7.1 Abdominal Distention/Cramping

Abdominal distention or cramping is defined as the presence of a tense abdomen, rigidity, guarding or rebound on exam.

For patients receiving trophic feeds, enteral feeds will be held for abdominal cramping or distention. Enteral feeding will be resumed at 20 kcal / hr in this group after 6 hours or improvement of distention or cramping, whichever occurs first.

When abdominal distention or cramping occurs in patients randomized to full-calorie feeding rates, the enteral feeding rate will be decreased by 25 cc / hr to a minimum rate of 10 cc / hr. The abdomen will be re-evaluated 6 hours later. If the distention or cramping is improved, the enteral feeds will be advanced to full-calorie rates per the full-calorie feeding protocol as long as GRVs are acceptable (see Appendix D). If, after 6 hours, the abdominal distention or cramping is not improved, then enteral feeding will be held and resumed at the 25 cc less/ hr rate after 6 additional hours or improvement of the abdominal distention or cramping, which ever occurs first

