5.1.4.1 Gastric Residuals -Trophic Feeding Group

GRVs will be checked every 12 hours while patients are receiving trophic feeding rates. If GRV remains less than or equal to 400 cc, GRV will be replaced and tube feeds will continue at 20 kcal / hr (see Appendix C). If GRV exceeds 400 cc, 400 cc of the residual volume will be replaced, tube feeds will continue at 20 kcal / hr and GRV will be rechecked in 2 hours. If GRV remains greater than 400 cc, tube feeds will be held. GRV will be replaced (up to 400 cc) and gastric residual rechecked every 2 hours. Tube feeds will continue to be held until residual volume is less than or equal to 400 cc. Once residual volume is less than or equal to 400 cc, trophic tube feeds will be restarted at a rate of 20 kcal / hr.

When the trophic feeding group is advanced to full-calorie enteral feeds (after 144 hours of trophic feeds), GRVs will be checked according to the full-calorie feeding protocol (see section 5.1.4.2 and Appendix D).

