5.1.4.2 Gastric Residuals – Full-calorie Feeding Group

Gastric residuals in the full-calorie feeding group will be checked every 6 to 12 hours according to the full-calorie feeding protocol (see Appendix D). If GRV remains less than or equal to 400 cc, GRV will be replaced tube feeds will be advanced or maintained if already at full-calorie rate. After the first episode of GRV greater than 400 cc, 400 cc of the GRV will be replaced, the feeding rate will be maintained at the current rate and residuals will be rechecked in 2 hours. After the second episode of GRV greater than 400 cc, tube feeds will be held. 400 cc of the GRV will be replaced and rechecked every 2 hours. Tube feeds will continue to be held until gastric residuals are less than 400 cc. Once GRV is less than or equal to 400 cc, GRV will be replaced and tube feeds will be restarted at 25 cc / hr less than the previous rate.

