5.1.7.5 Diarrhea

Diarrhea is defined as more than 3 liquid bowel movements totaling more than an estimated 500 cc in a 24-hour period.

Since diarrhea is rarely caused solely by enteral feeds (Kandil, 1993), the treatment of diarrhea may include discontinuation of laxatives and/or pro-kinetics, initiation of anti-diarrheals, treatment for C. *dificile* infection, or addition of fiber to the diet. The treatment will be determined by the patient's primary medical team, but will not include decreasing the enteral feeding rate unless the primary medical team feels that the patient's health is at risk because of the severity or nature of the diarrhea.

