5.1.7.6 Constipation

Constipation is defined as the absence of a bowel movement requiring a specific intervention (i.e. enema, laxative, disimpaction, etc.) at the discretion of the primary medical team.

The treatment will be determined by the patient's primary medical team, but will not include decreasing the enteral feeding rate unless the primary medical team feels that the patient's health is at risk because of the severity or nature of the constipation.

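### Section 5.1.7.1 handles rigidity, guarding or rebound like a tense abdomen: the full-calorie arm is fed for 6 hours before any hold, and in either arm a hold may end at 6 hours without improvement

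*Protocol*

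**What the plan says.** Protocol 5.1.7 standardizes the action for each gastrointestinal intolerance and leaves the primary team to decide whether a definition is met. For distention or cramping, 5.1.7.1 gives this definition: "Abdominal distention or cramping is defined as the presence of a tense abdomen, rigidity, guarding or rebound on exam". All four signs then follow the same path.

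- **Full-calorie arm.** First, "the enteral feeding rate will be decreased by 25 cc / hr to a minimum rate of 10 cc / hr". The abdomen is examined again 6 hours later. If it is better, feeds advance toward goal, provided residuals are acceptable. If it is not, feeds are "held and resumed at the 25 cc less/ hr rate after 6 additional hours or improvement of the abdominal distention or cramping", whichever comes first.
- **Trophic arm.** Feeds are held straight away and resumed at 20 kcal/hr "after 6 hours or improvement of distention or cramping, whichever occurs first".

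Other parts of the protocol bear on this. Section 4.3, exclusion 20, bars patients with bowel obstruction, ischemia or infarction. Section 9.2 says that early full-calorie feeding may raise the risk of intestinal ischemia or infarction. Section 9.6 counts the standardized responses to intolerance among the measures that minimize risk. Section 5.1.9 ends protocol feeding when an abdominal problem needs emergency surgery.

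**The concern.** A tense abdomen and peritoneal signs call for different caution. Rigidity, guarding or rebound can mark the same bowel conditions that exclusion 20 keeps out at entry. Followed to the letter, 5.1.7.1 does two things that are hard to defend for those three signs.

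1. The full-calorie arm continues to be fed for 6 hours before any hold, while the trophic arm is held immediately. The less cautious first step falls on the arm for which 9.2 names the ischemia risk.
2. In both arms the hold has a 6-hour ceiling. Because the earlier of time or improvement ends it, feeding can restart with the sign unchanged. The section does not say that the team may keep feeds off longer.

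What is at stake is patient safety in a small group, not the endpoint, the error rate or the estimate.

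**Working it through.** The plan gives no figure to reproduce here. The check traces the rule in time and compares it with the protocol's other feeding rules.

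**Inputs, all from 5.1.7.1.** Full-calorie: feed at 25 cc/hr less (floor 10 cc/hr) for 6 h, then hold for up to 6 h if not improved, then resume at the reduced rate. Trophic: hold for up to 6 h, then resume at 20 kcal/hr.

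**Assumptions.** The sign stays unchanged for 24 hours. The text does not say whether the rule starts again when the sign is still present at restart, so both readings are shown.

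| Reading | Full-calorie arm fed | Trophic arm fed |
|---|---|---|
| Re-applied at each restart | 0–6 h and 12–18 h: 6 + 6 = 12 h (held 6–12 and 18–24) | about 0 h (each restart triggers a new hold) |
| Applied once | 0–6 h and 12–24 h: 6 + 12 = 18 h (held 6–12) | 6–24 h: 18 h (held 0–6) |
| Proposed rule | 0 h | 0 h |

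The definition rests on a sign being present, so a patient who still has it at restart meets the definition again. Re-application is therefore the more natural reading, and under it the exposure sits almost wholly in the full-calorie arm. The rate may be low: at the 10 cc/hr floor, 12 h × 10 cc/hr = 120 cc.

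**Calories given up under the proposed rule.** Trophic arm: at most 18 h × 20 kcal/hr = 360 kcal of the daily 24 h × 20 kcal/hr = 480 kcal, or 75%, and about none under re-application. Full-calorie arm: 12 to 18 hours of reduced-rate feeding per 24 hours of persistent sign.

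**Comparison with the other feeding rules**

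| Section | When the hold ends, or what discretion exists |
|---|---|
| 5.1.4.1, residuals, trophic | On the condition, with no clock: "Tube feeds will continue to be held until residual volume is less than or equal to 400 cc" |
| 5.1.4.2, residuals, full-calorie | On the condition, with no clock: "Tube feeds will continue to be held until gastric residuals are less than 400 cc" |
| 5.1.7.2, aspiration, tube correctly placed | Fixed 6 h |
| 5.1.7.3, regurgitation with a high residual | Fixed 6 h |
| 5.1.7.4, vomiting | 6 h counted from the last episode, so it lengthens while vomiting continues |
| 5.1.7.5, diarrhea | No rate cut "unless the primary medical team feels that the patient's health is at risk because of the severity or nature of the diarrhea" |
| 5.1.7.6, constipation | The same exception, where "health is at risk because of the severity or nature of the constipation" |
| 5.1.7.1, distention or peritoneal signs | At most 6 h, improved or not; no exception stated in the section |

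The protocol thus already contains condition-based holds and a team exception. It also contains other timed holds.

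**The case against.** The case for leaving the rule alone has several parts, and some of it stands.

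- **The charts are missing.** The Appendix C and D flow charts are not shown, and 5.1.7.1 refers to Appendix D. A reader might infer that the protocol gives the team no override anywhere. The documents do not support that: a safeguard in the charts cannot be ruled out. The point is limited to what the section text says.
- **Timed holds are common.** A reader might see 5.1.7.1 as the odd one out. It is not: aspiration and regurgitation with a high residual also carry fixed 6-hour holds. The diarrhea and constipation exceptions are imperfect comparators too, because there the default is to keep feeding, whereas here it is already to reduce or hold. What remains is that no right to extend the hold is stated.
- **There are other routes.** The team classifies the event (5.1.7). Section 5.1.6 recognizes stops for reasons other than intolerance and sets no general restart time, so a stop for suspected ischemia could go that way. Section 5.1.9 covers emergency surgery, and Appendix F makes each investigator responsible for patient safety. These narrow the problem. They do not settle the case of a patient who meets the 5.1.7.1 definition, whose signs persist, and who does not need emergency surgery. Guarding or rebound meets that definition on its face, so using another route means not applying the section's own wording.
- **Exposure is easy to overstate.** A reader might take 18 of 24 hours in both arms as the size. That holds only if the rule is applied once and then ignored while the sign persists, which fits poorly with a definition based on the sign being present.

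**Conclusion.** The point holds as a patient-safety weakness in the written rule, mainly in the full-calorie arm. For rigidity, guarding or rebound, the section text continues feeding there for 6 hours before any hold. In both arms it lets the hold end at 6 hours without improvement.

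If the sign is unchanged for 24 hours, the full-calorie arm is fed for about 12 hours with re-application and 18 with a single application. The trophic arm is fed for about 0 or 18 hours. These are hours of exposure, not of harm: the documents give neither how often these signs occur nor how often injury would follow. The conclusion also depends on the unseen charts adding no hold rule.

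The different first step in the two arms might suggest bias in the treatment comparison. Nothing in the documents shows that, and it is not claimed. This is a recommended, inexpensive correction and not a threat to the trial's validity.

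**What to change.** Amend 5.1.7.1 as follows, and bring the bedside charts into line.

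1. For rigidity, guarding or rebound, hold feeds at once in both arms. Resume only when the sign has improved and the treating team judges it safe. The 6-hour clock does not apply to these signs, and no imaging is mandated.
2. Keep the existing rule for a tense abdomen alone.
3. State that the team may extend any hold under this section when restarting would put the patient at risk, in the spirit of the exception in 5.1.7.5.

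Section 5.1.9 need not be widened for this. Stopping protocol feeding for obstruction or ischemia managed without surgery is a separate question.

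The cost is a short amendment and the calories shown above for the affected patients, whose number the protocol does not give but who should be few. No procedures are added, and follow-up and the intention-to-treat analysis are unchanged.

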5.1.7.2 Aspiration

Aspiration is defined as the presence of food in the lungs. This will be determined by the primary medical team, but will include visualization of enteral feeds in the endotracheal tube or enteral formula suctioned from the endotracheal tube.

When aspiration occurs, the tube will be checked to confirm that it terminates in the correct location (gastric or post-pyloric). The manner in which the tube position is confirmed will be determined by the primary medical team, but will include either auscultation of air forced through the tube or obtaining a radiographic study. If the feeding tube terminates in the esophagus, it should be repositioned and tube feeds restarted at 25 cc / hr less than the previous rate (minimum of 10 cc / hr) for the full-calorie feeding group and 20 kcal / hr for the trophic feeding group. If the feeding tube terminates distal to the esophagus, enteral feeds will be held for 6 hours. After 6 hours, enteral feeds will be restarted at 25 cc / hr less than the previous rate (minimum of 10 cc / hr) for the full-calorie feeding group and 20 kcal / hr for the trophic feeding group.

5.1.7.3 Regurgitation

Regurgitation is defined as the presence of enteral feeds in the oropharynx or nasopharynx on routine oral care.

When regurgitation occurs, the tube will be checked to confirm that it terminates in the correct location (gastric or post-pyloric). The manner in which the tube position is confirmed will be determined by the primary medical team, but will include either auscultation of air forced

through the tube or obtaining a radiographic study. If the feeding tube terminates proximal to the stomach, it will be repositioned and enteral feedings will continue at the previous rate. If the tube is in the correct position (i.e. gastric or post-pyloric), a GRV will be checked. If the GRV is greater than 400 cc, the enteral feeds will be held for 6 hours. After 6 hours, the enteral feeds will be restarted at 25 cc / hr less than the previous rate (minimum of 10 cc / hr) for the full-calorie feeding group and 20 kcal / hr for the trophic feeding group. If the gastric residual is less than 400 cc, the residual will be replaced and the enteral feeds will continue at the current rate.

5.1.7.4 Vomiting

Vomiting is defined as the forceful expulsion of gastric contents from the oropharynx or nasopharynx.

When vomiting occurs, enteral feeds will be held for 6 hours. Six hours after the last episode of vomiting, enteral feeds will be restarted at 25 cc / hr less than the previous rate (minimum of 10 cc / hr) for the full-calorie feeding group, and 20 kcal / hr for the trophic feeding group.

The use of pro-kinetic agents and/or advancing the distal location of the feeding tube to a post-pyloric position should be considered in patients who experience vomiting.

5.1.7.5 Diarrhea

Diarrhea is defined as more than 3 liquid bowel movements totaling more than an estimated 500 cc in a 24-hour period.

Since diarrhea is rarely caused solely by enteral feeds (Kandil, 1993), the treatment of diarrhea may include discontinuation of laxatives and/or pro-kinetics, initiation of anti-diarrheals, treatment for C. *dificile* infection, or addition of fiber to the diet. The treatment will be determined by the patient's primary medical team, but will not include decreasing the enteral feeding rate unless the primary medical team feels that the patient's health is at risk because of the severity or nature of the diarrhea.

5.1.7.6 Constipation

Constipation is defined as the absence of a bowel movement requiring a specific intervention (i.e. enema, laxative, disimpaction, etc.) at the discretion of the primary medical team.

The treatment will be determined by the patient's primary medical team, but will not include decreasing the enteral feeding rate unless the primary medical team feels that the patient's health is at risk because of the severity or nature of the constipation.

5.1.7.7 Use of Prokinetic Agents

The use of prokinetic agents, including erythromycin and metoclopramide is not protocolized. Use of these agents will vary between centers and investigators. It is reasonable to administer these agents in a patient who experiences elevated GRV, aspiration, or vomiting, but the final decision is left to the discretion of the primary medical team. The use of prokinetic agents will be prospectively collected on the case report form.

5.1.8 Completion of Enteral Feeding Procedures

Patients will be considered to have completed the study enteral procedures if any of the following conditions occur:

- 1. Death
- 2. Hospital discharge
- 3. Alive 28 days after randomization
- 4. Extubation or 48 hours of UAB, whichever occurs first (see Definition of Unassisted Breathing, Appendix G)

5.1.9 Premature Withdrawal from Treatment

The feeding protocol will be discontinued in any patient who develops an abdominal process requiring emergent surgical exploration or repair, or an allergy to the enteral feeding formula. Data will continue to be collected prospectively in these patients until day 28 after randomization or hospital discharge, whichever occurs first.

5.5 Glucose Control

As levels of hyperglycemia are likely to vary with different volumes of enteral feeds and can confound the results of this study, glucose control protocols will be utilized to maintain tight control of hyperglycemia in all study patients. Each participating institution will utilize their own standard management, including institution-specific insulin drip protocols, to maintain blood sugars within at least a target range of 80-150 mg / dL. The use of protocols with tighter ranges of blood sugar control (i.e. 80-110 mg / dL) will be allowed at institutions where this is standard practice for the care of critically ill patients. After both the first 100 and 250 patients, the DSMB will evaluate the blood glucose levels for the trophic versus full-calorie feeding groups for the first 6 days of the study. If the blood glucose levels between the two groups are not adequately similar, the tight glucose control requirements may be adjusted in an attempt to make these values similar over the remaining course of the study.

5.6 Ventilator Procedures

Ventilator management, including weaning, will be a simplified version of the 6 ml / kg PBW lung protective ventilation protocol from ARDSNet Study 01 – ARMA (See Appendix G) (The Acute Respiratory Distress Syndrome Network, 2000). If not already being utilized, this low tidal volume protocol for mechanical ventilation must be initiated within one hour of randomization.

Since the time a patient achieves unassisted ventilation affects some secondary endpoints, and because recent evidence-based consensus recommendations have identified a best practice for weaning, a weaning strategy will also be controlled by protocol rules in accordance with these evidence-based recommendations. This will assure similar weaning methods and provide potential benefit to both study groups. This newer weaning strategy is a simplified version of the protocolized weaning strategy used in prior ARDS Network studies (see Appendix G, section G.2.).

5.7 On-Study Fluid Management

Fluid management during shock will be unrestricted. However, in patients not in shock, a conservative fluid approach will be required for all patients enrolled in the study. This conservative fluid management approach will represent a simplification of the algorithm utilized in the ARDS Network FACTT study (see Appendix H). If not already being utilized, this conservative fluid management approach must be initiated within four hours of randomization, and continued until UAB or study day seven, whichever occurs first.

5.8 Procedures After Re-Intubation

In the event patients are extubated but re-intubated within the 28-day treatment period, ventilator and feeding procedures should be resumed and continued through day 28.

6 Data Collection

6.1 Background Assessments

- 1. Demographic and Admission Data
- 2. Pertinent Medical History and Physical Examination
- 3. Height; measured Body Weight (mBW); calculated predicted body weight (PBW); body mass index (BMI)
- 4. Time on ventilator prior to enrollment
- 5. Type and location of ICU Admission
 - a. Medical
 - b. Surgical scheduled
 - c. Surgical unscheduled
 - d. Trauma
- 6. Risk factors for ALI/ARDS (sepsis, aspiration, trauma, pneumonia, drug overdose, other)
- 7. Presence of following chronic diseases:
 - a. Metastatic cancer (proven by surgery, computed tomographic scan, biopsy or other documented method)
 - b. Hematologic malignancy (ex: lymphoma, acute leukemia, or multiple myeloma)
 - c. AIDS with complications (ex: PCP pneumonia, Kaposi's sarcoma, lymphoma, tuberculosis, or toxoplasmosis).
- 8. Weight loss in the last 6 months

6.2 Baseline Assessments

The following information will be recorded during the 24-hour interval encompassing the 12 hours prior to randomization and the 12 hours after randomization. If more than one value is

available for this 24-hour period, the value closest to the time of enrollment will be recorded. If no values are available from the 12 hours prior to randomization, then values will be measured during the 12 hours post randomization and prior to initiation of enteral feeds.

- 1. Vital Signs: heart rate (beats / min), systemic systolic and diastolic BP (mmHg), body temperature (⁰C)
- 2. Ventilator mode, rate, minute ventilation, tidal volume, FiO₂, PEEP, plateau, peak, and mean airway pressures
- 3. Arterial pO₂, pCO₂, pH and SpO₂
- 4. Serum electrolytes, magnesium, phosphorous, BUN, creatinine, bilirubin, and glucose
- 5. Blood hemoglobin, hematocrit, WBC, and platelets, Prothrombin time (PT)
- 6. Serum total protein, albumin
- 7. Glasgow Coma Score
- 8. Frontal Chest Radiograph radiographic lung injury score (# of quadrants)
- 9. Administration of the following medications (Y / N):
 - (a) Sedatives
 - (b) Vasopressors
 - (c) Pro-kinetic agents (cisapride, metoclopramide, lactulose, sorbitol, or erythromycin)
- 10. Location of feeding tube (orogastric, nasogastric, oro-enteral, naso-enteral, PEG or jejunostomy tube)
- 11. Presumed site of infection, if sepsis is the etiology of ALI / ARDS
- 12. APACHE III score
- 13. Blood for DNA banking (appendix K)
- 14. Blood for cytokines, mediators, and markers of inflammation. Plasma obtained from two, 10 ml EDTA anti-coagulated blood samples will be divided immediately after centrifugation into 4 equal 2 ml aliquots in specified tubes and frozen at -70° C.
- 15. Urine for F₂- isoprostane metabolites. Urine obtained from the patients will be collected in an 8 ml sample tube and divided into 4 equal aliquots in specified tubes and frozen at 70°C.

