3.2 Secondary Endpoints

1. The secondary efficacy variable for the trial is mortality prior to hospital discharge with unassisted breathing. Patients alive in hospital at day 60 will be considered to have survived.

- 2. Mortality before hospital discharge home, with unassisted breathing, to day 90. Patients alive in hospital to day 90 will considered to have survived
- 3. Number of ICU-free days at 28 days after randomization
- 4. Number of organ failure-free days at 28 days after randomization. Organ failure will be defined by previously validated definitions for renal, circulation, central nervous system, hematologic, and hepatic organ and system failures (Bernard, 1997).

Organ failure is defined as present on any date when the most abnormal vital signs or clinically available lab value meets the definition of clinically significant organ failure according to the Brussels Organ Failure Table. Patients will be followed for development of organ failures to death, hospital discharge or study day 28, whichever comes first. Each day a patient is alive and free of a given clinically significant organ failure will be scored as a failure-free day. Any day that a patient is alive and free of all 5 organ failures will represent days alive and free of all organ failure. Central nervous system dysfunction is evaluated using the Glasgow Coma Scale.

- 5. Number of days between the day of first meeting criteria for weaning-readiness (see Appendix G, section G.2.) and day 28 after randomization.
- 6. Mortality and VFDs in patients with pre-randomization $PaO_2/F_1O_2 \le 200$.
- 7. Change in plasma levels of IL-6, IL-8, VWF, SPD, and total protein concentrations from baseline to study day 3.
- 8. Ventilator free days and mortality prior to hospital discharge with unassisted breathing to day 60 and number of ventilator-free days to day 28 in patients with shock (defined in 2.1.2) at the time of randomization.

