4.4 Enrollment, Randomization, and Study Initiation Time Window

All patients must be randomized within 48 hours of meeting inclusion criteria for ALI (inclusion criteria 1-3) and within 72 hours of initiating mechanical ventilation. The window for randomization will begin at the time of meeting all inclusion criteria and/or the time of documentation of mechanical ventilation, regardless of hospital location. The first three inclusion criteria may be met at either the Network or referring hospital. Following randomization, the low tidal volume protocol for mechanical ventilation must be initiated within one hour (if not already being utilized). Enteral feeds and the enteral feeding protocol must be initiated within 6 hours of randomization.

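### The baseline rule in Section 6.2 lets a post-randomization value replace an available earlier one, at odds with the section's own fallback

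*Protocol*

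**What the plan says.** Section 6.2 (Baseline Assessments) records baseline data over the "24-hour interval encompassing the 12 hours prior to randomization and the 12 hours after randomization". Two sentences then say which value counts.

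- **Several values in the window:** of those "available for this 24-hour period, the value closest to the time of enrollment will be recorded". There is no preference for the earlier side and no condition about feeding.
- **No earlier value:** "If no values are available from the 12 hours prior to randomization, then values will be measured during the 12 hours post randomization". A further condition in the same sentence limits these to samples taken before feeding begins.

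The list that follows includes "Arterial pO₂, pCO₂, pH and SpO₂" (item 3), with FiO2 in item 2. It also includes glucose (item 4), serum total protein and albumin (item 6) and the research plasma sample (item 14).

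Section 4.4 sets when study care starts: "the low tidal volume protocol for mechanical ventilation must be initiated within one hour (if not already being utilized" of randomization, and "Enteral feeds and the enteral feeding protocol must be initiated within 6 hours of randomization". Section 5.7 and Appendix H require the conservative fluid approach within four hours for patients not in shock.

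Section 3.2, item 6, defines a secondary endpoint as "Mortality and VFDs in patients with pre-randomization" PaO2/FiO2 of 200 or less. Section 7 uses the day-0 value as covariate when comparing day-3 IL-6, IL-8 and protein.

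**The concern.** A baseline value should describe the patient before the assigned treatment, and preferably before any study-mandated care. The closest-value sentence does not secure this even when a suitable earlier value is in the chart.

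The two sentences also protect patients unevenly. A patient with no earlier value must be sampled before feeds start. A patient who has an earlier value can have it replaced by a later one with no such limit. The fallback makes sense only if earlier values were meant to come first, yet the sentence before it does not say so. Section 6.2 also moves between enrollment and randomization as the reference time, so sites could anchor differently.

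Feeding is the randomized factor, and Section 5.5 itself expects hyperglycemia to vary with feeding volume. A glucose recorded after feeding has begun is a baseline that the assigned arm could already have influenced. Oxygenation recorded after the move to protocol ventilation may reflect study care rather than the presenting lung injury.

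**Working it through.** The protocol states no figure to reproduce here. The check compares the rules, then illustrates timing under stated assumptions.

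**1. The rule applied to one patient.** Suppose readings exist 2 hours before and 1 hour after randomization. The distances are 2 h and 1 h, so the later reading is recorded. The fallback sentence does not operate, because an earlier value exists, and its feeding limit does not apply.

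**2. What can start inside the post-randomization half of the window (0 to 12 h).**

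| Study care | Latest start after randomization | Source | Arms |
|---|---|---|---|
| Low tidal volume ventilation, if not already in use | 1 h | 4.4, 5.6 | both, same |
| Conservative fluids, if not in shock and not already in use | 4 h | 5.7, App. H | both, same |
| Enteral feeding protocol | 6 h | 4.4, 5.1.3 | differs by arm |

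All three deadlines lie inside the 12 hours.

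**3. How often a later value would be chosen (assumption: the documents give no sampling frequency).**

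*Regular draws every q hours.* The first draw after randomization comes at time u, uniform on 0 to q; the last draw before it was q − u hours earlier. The later one is chosen when u < q − u, that is u < q/2, which has probability 1/2. The share of all patients whose recorded value comes more than f hours after randomization is max(0, 1/2 − f/q).

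| q | later than 1 h | later than 4 h | later than 6 h |
|---|---|---|---|
| 4 h | 1/2 − 1/4 = 25% | 0% | 0% |
| 8 h | 1/2 − 1/8 = 37.5% | 1/2 − 4/8 = 0% | 0% |
| 12 h | 1/2 − 1/12 = 41.7% | 1/2 − 4/12 = 16.7% | 1/2 − 6/12 = 0% |

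*One value at a uniform random time on each side.* The later one is chosen in 50% of patients. It lies beyond 6 h with probability equal to the integral of (12 − b)/144 for b from 6 to 12, which is 18/144 = 12.5%.

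Simulation of both schemes agrees: 49.8% to 50.0% post-randomization in each, with 0% and 12.5% beyond 6 h respectively. The 1, 4 and 6 h marks are deadlines. Care may begin sooner, so the share after the actual start could be larger.

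**4. Conditional illustration for the 200 cut.** Take PaO2/FiO2 as normal with mean 155 and SD 73 (Table 3), and treat the values before and after randomization as bivariate normal with assumed correlation r. The cut is at z = (200 − 155)/73 = 0.616. The share falling on opposite sides of 200 is 2·[Φ(z) − Φ₂(z, z; r)].

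| r (assumed) | opposite sides of 200 | × 1/2 post-randomization |
|---|---|---|
| 0.7 | 20.7% | 10.4% |
| 0.8 | 16.8% | 8.4% |
| 0.9 | 11.8% | 5.9% |

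The last column is about 6% to 10% of patients. It applies only if the subgroup ratio is read from the Section 6.2 record.

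**The case against.** A reader might infer that Section 6.2 contradicts secondary endpoint 6 and misplaces 6% to 10% of patients. The documents do not support that. Section 3.2 already specifies a pre-randomization ratio, and nothing says it is taken from the 6.2 record. Inclusion criterion 1 (Section 4.2) and the 48-hour window (Section 4.4) mean that every enrolled patient has a qualifying PaO2/FiO2 before randomization, which could be used instead. If it is, the figure is zero. The correlation and the even timing are also assumptions, and Table 3 does not label 155 and 73 as baseline values.

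A reader might also infer that severity scores and covariates in general are contaminated. That goes too far:

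- The APACHE III footnote in Appendix E refers to labs from the 24 hours before randomization.
- Shock, a factor in the primary model, is a randomization stratum (Section 4.6) and so is known before assignment.
- IL-6 and IL-8 come from a scheduled day-0 research draw, so the several-values rule has little to act on. A draw made after randomization falls under the fallback and must precede feeds.
- Section 3.2, item 7, speaks of plasma total protein, while Section 6.2, item 6, lists serum. Protein is exposed only if the routine value is the one used.
- Glucose is a baseline item, but Section 7 does not name it as a covariate.

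Nor is a biased treatment comparison shown. Ventilation and fluid rules are common to both arms. A closest-value rule also favors readings near randomization, so a value taken after all three kinds of care have begun would be unusual under regular sampling.

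These limits stand and reduce the weight of the point. They do not remove the conflict between the two sentences in 6.2. Nor is the matter one for the statistical analysis plan alone: the rule decides which value sites write down, and an analysis plan cannot use an earlier value that was not recorded.

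**Conclusion.** The point holds as a flaw in a recording rule. As written, Section 6.2 can replace an available pre-randomization value with one taken after study care, including the randomized feeding, has begun. Its own fallback implies the opposite priority.

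The consequence is minor. The primary comparison of ventilator-free days is untouched. What is exposed is the description of patients at baseline, any day-0 covariate drawn from routine measurements, and the PaO2/FiO2 subgroup if, and only if, it reads this record. Its size cannot be derived from the documents. The one-half figure rests on evenly spread sampling. The 6% to 10% figure also needs the unstated data source, the assumed correlation and Table 3's mean and SD, so it is an illustration and not an estimate of misclassification.

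**What to change.** In Section 6.2:

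1. Record the last value before randomization.
2. Use a post-randomization value only if none exists in the prior 12 hours, and only if it was taken before the first study feed.
3. Use randomization as the single reference time throughout the section.

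In Section 3.2, item 6, state that the subgroup uses this pre-randomization PaO2/FiO2, or the qualifying eligibility value where the recorded baseline is post-randomization.

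The cost is a revised case report form instruction and two edits to the text. No new measurements are needed.
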